### 1.1. Background

**Smoking During Pregnancy is a Major US Public Health Problem:** Smoking during pregnancy is a major modifiable cause of poor pregnancy and child health outcomes in the US (1, 2). Maternal smoking increases the risk of a number of serious adverse outcomes of pregnancy, including spontaneous abortion, placental complications, preterm delivery, and fetal and neonatal death. The most consistent adverse effect of smoking during pregnancy is low birth weight (LBW, i.e., <2500 g) (1, 24, 25), the risk of which doubles with maternal smoking (2). In turn, LBW (particularly very low birth weight, i.e., <1500 g), exponentially increases morbidity and mortality risk (3). In the US, maternal smoking is responsible for 30% of LBW babies, 10% of premature deliveries, and 5% of infant deaths (7). Fortunately, smoking cessation by 16 weeks gestation (9, 10), or as late as the third trimester (10), results in a near-normal birth weight infant. Reductions in smoking also increase birth weight (26). Despite these risks, the majority of women who are smoking at the time of their first prenatal visit continue to smoke, risk factors for which include being unmarried, less educated, heavier smokers (>1/2 pack per day), depressed, with partners who smoke (27-30).

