### 5.3. Method for Assigning Participants to Treatment Groups

Participants will be randomly assigned to one of two treatment conditions: Bupropion 300 mg/day (n = 180) or placebo (n = 180). We will use small-block randomization by site (Penn or MATER) provided by [name], the study biostatistician. A PHQ-9 score of 10 or greater will be used to identify major depression and stratify the randomization on it. Study site (Penn or MATER) will be the second of the two stratification variables. Study staff and the Investigational Drug Service (IDS) staff will be responsible for medication randomization. The process for randomization is: 1) The research coordinator will complete a “randomization form,” which includes the variables to be entered into the randomization program and fax or email the form without protected health information to the UPenn site; 2) A designated study staff member

Table 1: Medication Dispensing Schedule

	Medication Dispensed For	Morning Dose	Evening Dose	Total Daily Dose
Visit A: Screening	N/A	No medication	No medication	
Visit B: Baseline	Wk 1	150 mg	No medication (for first 3 days); then 150 mg	150 mg
Visit C: Wk 1	Wk 2 through Wk 5	150 mg	150 mg	300 mg
Visit D: Wk 3	N/A	N/A	N/A	N/A
Visit E: Wk 5	Wk 6 through Wk 10	150 mg	150 mg	300 mg
Visit F: Wk 7		150 mg	150 mg	300 mg
Visit G: Wk 10	Endpoint	No medication	No medication	N/A

CONFIDENTIAL

This material is the property of the University of Pennsylvania. Do not disclose or use except as authorized in writing by the study sponsor

Visit H: Wk 24 Post-TQD	N/A	No medication	No medication	N/A
Visit I: 2 wk postpartum	N/A	No medication	No medication	N/A
Visit J: 6 wk postpartum	N/A	No medication	No medication	N/A

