## 7. Statistical Plan

### 7.1. Power

A power analysis is provided only for the primary aims because the exploratory aim is hypothesis generating. Most of our power calculations were approximated as 2-sided t- or z-tests, with  $\alpha = 0.05$ , using PASS Software (Power and Sample Size, NCSS Software, Kaysville, UT). Equivalence testing was approximated as two one-sided tests, with  $\alpha = 0.025$  each.

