For **H3**, we have very high power. Oncken et al. (47) found a difference in birth weight between groups of 337 g, which yields an effect size  $> d=0.5$ . The power to detect a difference of that magnitude will exceed 99%, and we have 80% power to detect a difference as small as 180 grams. We also have >89% power to detect differences in secondary analyses of the frequency of low birth weight and preterm delivery.

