**H2:** We will compare treatment arms for equivalence of the frequency of moderate-to-severe AEs (individual and total). The hypothesis test for equivalence is a test of whether the OR is out of the prescribed range for the difference between the treatment arms. Using logistic regression, we will conduct two one-sided tests against predefined upper and lower equivalence boundaries on percent reporting only mild AEs. The test-statistic will be the z-score corresponding to the log of the OR. This provides a more valid test of the potential safety of bupropion for pregnant smokers than a simple comparison of mean responses on a measure of AEs.

**H3:** Mean birth weight will be compared for treatment groups using a two-sample t-test, in the context of multiple linear regression. The regression format allows us to add covariates to adjust for imbalances in participant characteristics between treatment arms. Treatment will be entered as a binary indicator. In a secondary analysis, we will also compare the percentage of participants in each group that delivers an infant of LBW (1500-2500 g) or preterm delivery. These secondary hypotheses will be tested using the z-score corresponding to the OR that will be estimated using logistic regression.

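### The low-birth-weight comparison has a 1500 g floor, so the lightest infants count as not low birth weight and a shift below 1500 g would look like benefit

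*Combined protocol and SAP*

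**What the plan says.** Section 7.2.2 tests H3 first on the mean: "Mean birth weight will be compared for treatment groups using a two-sample t-test, in the context of multiple linear regression". It then adds a secondary analysis to "compare the percentage of participants in each group that delivers an infant of LBW (1500-2500 g) or preterm delivery", and says of it: "These secondary hypotheses will be tested using the z-score corresponding to the OR that will be estimated using logistic regression".

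Section 1.1 uses the same abbreviation differently: "low birth weight (LBW, i.e., <2500 g", with no lower limit. The next sentence treats very low birth weight as part of that category and as its worst part: "LBW (particularly very low birth weight, i.e., <1500 g), exponentially increases morbidity and mortality risk".

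Section 7.1.1 claims more than 89% "power to detect differences in secondary analyses of the frequency of low birth weight and preterm delivery" but gives neither a weight band nor assumed rates. Section 3.2 lists the birth outcomes to be abstracted, including birth weight, gestational age, preterm birth, small for gestational age and NICU admission. It defines no category under 1500 g. Nowhere do the documents say how infants under 1500 g are handled in the low-birth-weight comparison.

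**The concern.** A binary birth-weight outcome should never improve when an infant gets lighter. With a floor at 1500 g, this one does: crossing the floor downwards removes the infant from the event count, and the arm's rate falls.

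That matters because harm to the fetus is an open question in this trial. Section 1.5 says the drug could adversely affect the developing fetus, Section 1.3 reports reduced fetal weights in animals, and Section 7.1.1 lists birth weight among the key birth outcomes for safety. A tail outcome is there to show what a mean dilutes. This one discards the end of the tail that matters most and credits the arm in which those infants occur.

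**Working it through.** **Inputs from the documents.** Arms: "Bupropion 300 mg/day (n = 180) or placebo (n = 180" (Section 5.3). Testing: two-sided, alpha 0.05 (Section 7.1). Birth weight in the cited nicotine gum trial (Section 1.1): 3287 g (SD 569) on gum and 2950 g (SD 657) on placebo.

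**Step 1: the plan's own H3 figures.**
- Pooled SD = √[(569² + 657²)/2] = 614.6 g. SE of the difference = 614.6 × √(2/180) = 64.8 g.
- For 337 g: d = 337/614.6 = 0.55 and power is 99.9% (stated: above 99%).
- For 180 g: Φ(180/64.8 − 1.96) = Φ(0.82) = 79.3% (stated: 80%).
- Both agree with the plan. The figure above 89% for low birth weight cannot be reproduced, because no rates are given.

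**Step 2: how many infants the floor removes (normality assumed).**
- Placebo: P(<1500) = Φ((1500 − 2950)/657) = 0.0137, and 0.0137 × 180 = 2.5 infants. P(<2500) = Φ((2500 − 2950)/657) = 0.247. The floor removes 0.0137/0.247, about 5.5% of the infants under 2500 g.
- Active arm of the cited trial: P(<1500) = 0.0008 and P(<2500) = 0.083.

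**Step 3: direction of the error (assumed counts).** Take 27/180 infants under 2500 g in each arm, with 2 under 1500 g on placebo and 8 on bupropion.

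| Outcome | Placebo | Bupropion | OR |
|---|---|---|---|
| Under 2500 g | 27/180 = 15.0% | 27/180 = 15.0% | 1.00 |
| 1500–2500 g, as written | 25/180 = 13.9% | 19/180 = 10.6% | 0.73 |
| Under 1500 g | 2/180 = 1.1% | 8/180 = 4.4% | 4.14 |

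The risk ratio as written is 19/25 = 0.76, an apparent 24% reduction. For the OR, ln(0.73) = −0.312 and SE = √(1/19 + 1/161 + 1/25 + 1/155) = 0.324, so z = −0.96.

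If infants under 1500 g were dropped from the denominator instead, the OR would be (19/153)/(25/153) = 0.76, in the same direction.

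**Step 4: larger assumed shifts.** Take 36/180 under 2500 g in both arms, with 4 under 1500 g on placebo. The OR for under 2500 g is 1.00 throughout.
- Ten more infants under 1500 g on bupropion (14): OR as written = (22/158)/(32/148) = 0.64, z = −1.47. OR for under 1500 g = (14/166)/(4/176) = 3.71, z = 2.27.
- Fifteen more (19): OR as written = (17/163)/(32/148) = 0.48, z = −2.27, a nominally significant false benefit.

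**Step 5: does removing the floor cost power?** Power = Φ{[|p₁ − p₂| − 1.96√(2p̄(1 − p̄)/180)] / √[(p₁(1 − p₁) + p₂(1 − p₂))/180]}, with rates from Step 2.
- Under 2500 g: 24.7% versus 8.3%, power 98.8%.
- 1500–2500 g: 23.3% versus 8.2%, power 97.7%.

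**The case against.** The strongest counter-argument is about reach. This is a secondary analysis under the hypothesis that bupropion raises birth weight. Several other outcomes keep infants under 1500 g: mean birth weight, preterm delivery, gestational age, small for gestational age, NICU admission and neonatal serious adverse events. The trial's overall safety reading does not hang on this odds ratio. That stands, and it limits the importance of the point. The mean is a weak safeguard, however: ten infants each 900 g lighter (an assumed drop) move the arm mean by 10 × 900/180 = 50 g, against a detectable 180 g.

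Second, the plan does not state that infants under 1500 g are non-events. They might be excluded, or counted through prematurity if low birth weight and preterm delivery form one composite. Exclusion leaves the bias in the same direction (Step 3). The composite reading is unlikely, because Section 7.2.2 speaks of hypotheses in the plural and Section 7.1.1 names the two outcomes separately. Even a composite would miss a term infant under 1500 g.

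Third, the sizes are constructed. This is fair. The 15% rate in Step 3 is below the 24.7% implied by the cited placebo figures, the equal totals are chosen for clarity, and the Step 3 contrast is not significant. The false significant benefit in Step 4 needs 15 shifted infants, about six times the 2.5 expected per arm. A shift straight from 2500 g or more to under 1500 g would read as no change rather than benefit, though the harm would still be missed.

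**Conclusion.** The point holds. The analysis definition contradicts the plan's own definition in Section 1.1, and as written the outcome can improve as birth weight worsens. That conclusion rests on the text alone.

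The size is uncertain and probably modest: about 2 to 3 infants per 180 at the cited placebo mean and SD, assuming normality, which is only a rough guide in the tail. The odds ratios in Steps 3 and 4 show direction and are not forecasts. The consequence is one misleading secondary odds ratio, not a compromised primary result. It should be corrected because the error favours the arm with the lightest infants.

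**What to change.** In Section 7.2.2, define low birth weight as birth weight under 2500 g with no lower bound, matching Section 1.1. Add the number and percentage of infants under 1500 g by arm as a descriptive category; counts will be too small for a useful test. In the same sentence, make clear that low birth weight and preterm delivery are two separate outcomes.

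The cost is one phrase plus a table row. Birth weight is already abstracted from delivery records, and under the Step 5 assumptions power does not fall (98.8% against 97.7%). The change should be made before unblinding.

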### **7.2.3. Specific Aim 2: Assess changes in depression symptoms and craving as mediators of bupropion's effect on quit rates.**

We will use a regression-based path model approach to examine mediation of treatment effects based on MacKinnon et al. (175). All variables will be standardized for the analyses. The two suspected mediators will be entered as standardized pre-post differences, continuously distributed and treated as normal in linear regression. The effects of treatment arm on

CONFIDENTIAL

mediators, and of mediators on outcome, will be assessed using linear regression and standardized variables. We will focus on changes in mediators from baseline to week 3, since abstinence-induced withdrawal effects typically peak within the first 3 weeks of cessation (174), but we can examine delayed changes to weeks 5, 7, and 10 as well. Assuming that treatment predicts our mediators, we will then assemble the path model using standard structural equation modeling approaches. The path model partitions the effect of treatment on outcome into direct (and unexplained) effects vs. mediated effects. We will then test the overall mediation hypothesis using the proportion of treatment effect explained (171-172), and the strength of each mediating pathway. To do this, we will estimate the model for standardized treatment predicting abstinence without mediators to estimate the direct effect of treatment in the unadjusted model ( $\hat{\beta}^{\dagger}$ ). We will then test whether treatment predicts each of the suspected mediators and, in turn, test whether mediators predict abstinence in an adjusted treatment model and estimate the effect of treatment in the mediator adjusted model  $\hat{\beta}^*$ . Finally, we will calculate the proportion of treatment effect explained, which is calculated as  $(\hat{\beta}^{\dagger} / \hat{\beta}^*)$ ; the standard error for this quantity is calculated using the delta method, and the mediation hypothesis will be tested using a z-test. Individual pathways will be tested using products of the coefficients along each path using a delta-method based z-test.

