#### Mediators and Moderators of Bupropion Response

##### **Depressive Symptoms and Craving as Mediators of Bupropion's Therapeutic Effects:**

Pregnant smokers who are depressed are less likely to quit smoking than those who are not (28). In pregnant minority women, even mild depression nearly doubled the risk of continued smoking (56). Thus, we expect that, given bupropion's well-established antidepressant effects (57, 58), its efficacy as a treatment for ND will be mediated by reductions in depressive symptoms. Likewise, several symptoms that are present in pregnant smokers before quitting smoking (e.g., irritability, anxiety, difficulty concentrating, insomnia, restlessness, increased appetite, depressed mood, drowsiness) are similar to those that occur commonly during nicotine withdrawal (59). Compounded by nicotine withdrawal, these symptoms may make it more difficult for pregnant women to quit smoking (34). Because bupropion mitigates craving associated with nicotine abstinence, we expect that its efficacy in treating ND in pregnant women will also be mediated by a reduction in craving.

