#### **6.5 Visit D: Week 3 (Approximately 25 minutes by telephone or in person)**

Participants will be asked to complete the PHQ-9 and the TLFB by telephone. They will then receive a 10-minute booster counseling session that focuses on reinforcing success and reviewing the quit plan (for participants who have quit smoking) or re-establishing a quit date

CONFIDENTIAL

and restarting the cessation process (for participants who have relapsed to smoking). The counseling schedule reflects the changing needs of the pregnant smoker during the course of pregnancy and smoking cessation (155), with more intensive help offered in the earliest phase of treatment and continued efforts to prevent relapse in the later stages.

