### **7.1.2. Aim 2:**

Analyses here will assess changes in craving and depression symptom scores as mediators of bupropion treatment effects at weeks 10 of treatment and 24 weeks post-TQD. These measures are continuous difference scores. Our sample of 360 is well above the minimum sample of 200 recommended for such analyses (169-170). The mediation hypotheses will examine the proportion of variance in treatment effect explained (171-172), and we will test each mediation hypothesis with a z-score generated using the delta method. Our sample of 360 gives us 80% power to observe small effects in a 1-sample test ( $\delta = 0.16$ ) when testing at  $\alpha = 0.05$ . There are 2 proposed mediating pathways (depression and craving) between treatment and outcome, so our type-1 error will be corrected to 0.025. A sample of 360 gives us 80% power to detect small-to-medium effects ( $\delta=0.35$  SD) for changes in the proposed mediators, which we have seen in previous trials (15, 52).

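### Aim 2 enters the mediators as change scores and names no baseline covariate, which weakens the mediator-to-abstinence path if the follow-up level, rather than the change, drives quitting

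*Combined protocol and SAP*

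**What the plan says.** Section 7.2.3 gives the form of both mediators: "The two suspected mediators will be entered as standardized pre-post differences, continuously distributed and treated as normal in linear regression". It adds "All variables will be standardized for the analyses". Section 7.1.2 agrees: "These measures are continuous difference scores". The change score is used both for arm to mediator and for mediator to abstinence, and each pathway is tested as follows: "Individual pathways will be tested using products of the coefficients along each path using a delta-method based z-test". On alpha, 7.1.2 says "There are 2 proposed mediating pathways (depression and craving) between treatment and outcome, so our type-1 error will be corrected to 0.025".

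No baseline PHQ-9 or QSU term is named in either Aim 2 model, although Table 2 collects both at Visit B. The general rules in 7.2 and 7.2.1 add a variable only if it turns out to be related to arm, to completion of follow-up or to missing data. Section 5.3 stratifies randomization on a PHQ-9 score of 10 or more, but Aim 2 does not list that factor as a covariate.

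On timing, 7.2.3 says "We will focus on changes in mediators from baseline to week 3". For the week-3 visit, section 6.5 says "Participants will be asked to complete the PHQ-9 and the TLFB by telephone". Table 2 shows the QSU at baseline and weeks 1, 5 and 10 only.

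**The concern.** A change score usually correlates negatively with its own baseline: women who start high tend to fall most. If women who start high also tend to stay relatively high and quit less, a large fall is mixed up with a poor prognosis, and regressing abstinence on change alone understates what the mediator does. Randomization protects the arm-to-mediator path from this bias but not the mediator-to-abstinence path, because change in the mediator is not randomized. Stratifying on PHQ-9 balances the arms and does not help the second path either.

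The product test and the proportion-explained measure both rest on that path. Aim 2 could therefore report no mediation by depression or craving when mediation is present. The Aim 1 efficacy and safety comparisons are not affected.

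**Working it through.** **The plan's own power figures.** For the 0.35 SD effect with 180 per arm, power = Φ(0.35 × √90 − z).
- At alpha 0.025 this is Φ(3.32 − 2.24) = 86.0%; at 0.05 it is 91.3%. The plan states 80%.
- For the one-sample effect of 0.16, power = Φ(0.16 × √360 − z). This is 85.9% at the printed alpha of 0.05 and 78.7% at 0.025.

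The stated 80% is therefore met or nearly met, but neither figure is the power of the product test, so neither bears on this point.

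**The restriction.** Let M0 and M1 be the baseline and follow-up mediator, with D = M1 − M0. Suppose abstinence has slope b on M1 and g on M0. Then

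b·M1 + g·M0 = b·D + (b + g)·M0.

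Leaving M0 out is correct only if g = −b. With M0 in the model, the coefficient on D is b for any g, the same as the coefficient on M1.

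**Size of the attenuation.** Set the baseline SD to 1, the follow-up SD to k and the correlation to r. The slope on D alone is

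b + (b + g)(rk − 1)/(k² + 1 − 2rk).

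- At k = 1 this is (b − g)/2 for any r: b/2 when g = 0, 0.75b when g = −b/2, and b when g = −b.
- At g = 0 the fraction of b retained is (k² − rk)/(k² + 1 − 2rk). For example, at k = 0.8 and r = 0.5 it is 0.24/0.84 = 0.29.

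| k | r = 0.3 | r = 0.5 | r = 0.7 |
|---|---|---|---|
| 0.8 | 0.35 | 0.29 | 0.15 |
| 1.0 | 0.50 | 0.50 | 0.50 |
| 1.25 | 0.66 | 0.71 | 0.85 |
| 1.5 | 0.77 | 0.86 | 1.04 |

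Standardizing rescales the coefficient and leaves the z-test unchanged. At k = 1 and g = 0 the z-statistic of this path falls to 0.62, 0.58 and 0.54 of its baseline-adjusted value at r = 0.3, 0.5 and 0.7.

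**Precision of arm to mediator.** At k = 1 the residual variance is 2(1 − r) without baseline and 1 − r² with it: 1.00 against 0.75 at r = 0.5.

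**Power of the product test, by simulation.**
- From the plan: N = 360, alpha 0.025 (taken as two-sided), arm effect 0.35 SD (applied in follow-up SDs), linear models.
- Assumed: logit slope 0.5 per baseline SD, r = 0.5, and the values of k and g.

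| Case | Without baseline | With baseline |
|---|---|---|
| k = 1, g = 0 | about 17% | about 70% |
| k = 0.8, g = 0 | 2% | 47% |
| k = 1.25, g = 0 | 57% | 84% |
| k = 1.5, g = 0 | 83% | 89% |
| k = 1, g = −b/2 | 43% | 71% |
| k = 1, g = −b (only change matters) | about 70% | about 70% |

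**Sensitivity.** Holding the arm effect at 0.35 baseline SDs, k = 1.25 gives 34% vs 62%. A weaker slope of 0.3 at k = 1 gives 4% vs 24%. A second simulation set abstinence at 28.5% on average and its effect as a risk difference per follow-up SD. At k = 1 and r = 0.5 it gave 17% vs 70% for 0.10 per SD and 6% vs 34% for 0.07.

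**The case against.** The strongest reply is that Aim 2 is about change: it sets out to assess changes in symptoms as mediators. If change itself drives quitting, the change score is the right variable and is not attenuated. That stands, and it makes the whole point conditional. But the change-only model assumes g = −b without testing it, whereas a model with baseline covers that case and the others.

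The Background gives some reason to doubt the assumption for depression: "Pregnant smokers who are depressed are less likely to quit smoking than those who are not". If only change mattered and rk were below 1, women with higher baseline scores would be expected to quit more. If higher baseline goes with less quitting overall, then g is above −rkb and less than k²(1 − r²)/(k² + 1 − 2rk) of the path is retained: less than 0.75 at k = 1, r = 0.5. A reader might go further and infer that baseline depression lowers quitting over and above the follow-up level, which would cut the path below half. The sentence does not support that. It is an overall association, compatible with g = 0 or moderately negative g, and it says nothing about craving.

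Adjustment is also not free in every configuration. In the second simulation at k = 1.5, r = 0.7 (0.10 per SD), power was 70% without baseline and 66% with it. When only change matters, adjusting sharpens the arm-to-mediator path and blunts the other. Take k = 0.8, r = 0.5 and an arm effect of 0.35 baseline SDs. The variance of D given arm is 0.84, and 0.48 given baseline too. Using 0.35√(90/V) for the first path and 0.5√(360 × 0.285 × 0.715 × V) for the second, the z-values are 3.62 and 3.93 without baseline, and 4.79 and 2.97 with it. The product z is about 2.66 against 2.52, or roughly 66% against 61% power at the 2.24 cut-off. That cost is small beside the losses it guards against.

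Finally, the covariate rules in 7.2 and 7.2.1 could bring the baseline scores in. They might, but only by chance association with arm or through a link with completion or missingness, so they do not secure it.

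**Conclusion.** The point holds conditionally. Aim 2 specifies change scores and names no baseline covariate. If the follow-up level drives abstinence and baseline has no separate effect, the mediator-to-abstinence path is halved at equal SDs, and in the simulated case product-test power drops from about 70% to about 17%. The loss is larger if the follow-up SD is smaller than the baseline SD, smaller if it is larger, and nil if only change matters. Of the inputs, only N, alpha and the 0.35 SD effect come from the plan. The slope, the correlation, the SD ratio and the baseline effect are assumptions, and 17% vs 70% is one point in a wide range.

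Three stronger readings are not supported:
- That the path is always at least halved. This needs a follow-up SD no larger than the baseline SD and no baseline effect of opposite sign to the follow-up effect; the documents give neither SD.
- That the scores are raw. The text says they are standardized, which leaves the test unchanged.
- That baseline is excluded. The plan is silent on it, apart from the conditional rules.

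Separately, the week-3 focus can apply only to the PHQ-9 as scheduled, because no week-3 QSU is collected.

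**What to change.** In 7.2.3, prespecify the mediator's own baseline value (PHQ-9 or QSU at Visit B) as a covariate in both the arm-to-mediator and the mediator-to-abstinence models, at whichever follow-up visit is used. The change score may stay: with baseline in the model it gives the same unstandardized coefficient and test as the follow-up value. Section 7.1.2 then needs at most a mention of the covariate.

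Also reconcile the week-3 focus with section 6.5 and Table 2, either by naming a visit at which the QSU is scheduled for the craving pathway or by adding the QSU at week 3.

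The covariate costs a wording change and one already collected variable per model. Naming another visit for craving is also wording only; adding a week-3 QSU would mean one more 10-item questionnaire at that contact.
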